### ***C2 Rationale for the Selection of Outcome Measures***

The feasibility outcomes will inform future studies if Adapted LiFE has the potential to reduce barriers for implementation. Outcomes have been selected based on literature review and the preclinical pilot study (see D1 for preliminary data). The feasibility outcomes were selected based on the Reach, Efficacy, Adoption, Implementation, and Maintenance (RE-AIM) framework including reach, acceptance, adherence, fidelity, safety, and appropriate efficacy measurement selection. Preliminary efficacy outcomes of balance, muscle strength, and habit formation measures are selected based on literature review on fall prevention and evidence-based exercise interventions for older adults.

## **D Investigational Agent**

### ***D1 Preclinical Data***

[figure not shown]
We conducted a mixed method study to adapt LiFE initially. The mixed-methods study consisted of two phases. At the first phase, a qualitative study was conducted to explore

stakeholders' opinion towards LiFE that included medically underserved older adults and occupational therapists (OT). Themes regarding intervention acceptance and concerns were used to adapt LiFE materials. Based on the themes emerging from the qualitative study, two changes to the LiFE user manual were made in the initial adaptation of LiFE. First, a graph explaining why fall prevention is important and how LiFE works was added to the beginning of user manual. We also reduced the number of words and pages by replacing text information with pictures in the manual. Second, pictures of African American older adults were used to reflect the demographic characteristics of medically underserved older adults in the city of St. Louis.

At the second phase, a single-group pilot study was conducted to test the feasibility of Adapted LiFE (Figure 1). Feasibility outcomes were selected based on the Reach, Efficacy, Adoption, Implementation, and Maintenance (RE-AIM) framework to evaluate initial Adapted LiFE (Table 1). Eight medically underserved older adults were recruited by convenience sampling from one senior apartment building in a health provider shortage area. Inclusion criteria were: (1) age 60 or older; (2) living independently; and (3) self-reported a slip, trip or fall in the past 12 months or were "concerned or worried about falling in the future." Exclusion criteria were: (1) Short Blessed Test score  $\geq 10$ , indicating cognitive impairment consistent with dementia; (2) inability to stand independently with a walking device; and (3) a serious health condition for which exercise is contraindicated. Participants were recruited through flyers and information sessions held in the senior apartment building. After consent, an occupational therapist would conduct a pre-test of preliminary efficacy outcomes and then start the first session of Adapted LiFE. Once participants completed all 7 sessions, a post-test was conducted by the OT immediately after the last in-home intervention session. The result showed that Adapted LiFE demonstrated good feasibility among the target participants. Eight older adults completed the pilot study (mean age  $66.4 \pm 5.6$ , 4 males, 3 African Americans, 5 Caucasians). The recruitment rate was 44% (11 enrolled out of 25 screened). The retention rate was 89% (8 completed out of 9 enrolled). Participants had high acceptance of adapted LiFE with a mean satisfaction score of  $6.89 \pm 0.38$ . The average adherence rate was 81.3%. For fidelity, 98% of components were delivered during the intervention period.

Thus, we regard the Adapted LiFE has the potential to have high acceptance and adherence rate among medically underserved older adults. Future studies should aim to evaluated the efficacy of Adpated LiFE with larger trials.

Figure 1 Overview of single group pilot study

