### **E1 Overview of Study Design**

The pilot study will use RCT with an attentional control design (Figure 2). The purpose of the pilot study with the same design as the future main study is to test the study protocol, estimate recruitment/retention rate, and validate tools. This study design is appropriate for a future larger study because Adapted LiFE has strong face validity, good feasibility, and minimal risk when compared with structured exercise programs for medically underserved older adults.

We will recruit 16 participants and randomize them to receive 7 sessions of home visit and 1 booster phone call one month after the last session of Adapted LiFE or attention control (AC) intervention. Once an eligible participant is screened and consented in his/her home (T0 visit), the OT interventionist will either conduct or schedule the pre-test (T1). All pre- and post-tests will be conducted in participants' homes. After T1, the OT interventionist will randomize the participants to Adapted LiFE or the attention control group. The intervention period will start immediately after randomization and consist of seven sessions over 12 weeks. Post-tests (T2) will be conducted by a blinded OT rater after the last intervention session at the participant's home. Phone follow-ups (T3) will be conducted one month after post-test by a blinded OT rater. Any additional questions from the participants will also be addressed in the phone follow-up.

Feasibility outcomes such as reach, adherence, fidelity, and safety will be evaluated throughout the study session. Efficacy outcome such as balance and muscle strength will be evaluated at pre- test (T1), and post-test (T2). Habit formation will also be evaluated at T1, T2, and 1-month after post-test via phone.

*Figure 2. Overview of the feasibility pilot study*

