### **E2 Subject Selection and Withdrawal**

#### **2.a Inclusion Criteria**

Medically underserved older adults will be recruited by convenience sampling. Referrals from OT staff and members of a community advisory board of the Participation,

---

Environment & Performance Laboratory (PEPL) will be the main channels for recruiting medically underserved older adults. Inclusion criteria include:

- (1) age 70 or older;
- (2) live independently;
- (3) live in a medically underserved/health professional shortage area;
- (4) self-report two falls or one injurious fall in the past 12 months. The definition of a fall and injurious fall are described in Table 4.

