# **I Study Administration**

## **I1 Organization and Participating Center**

The clinical translational research of the Participation, Environment and Performance Laboratory (PEPL) focuses on the unique contribution that the environment can make toward improving the performance, participation and quality of life for persons living with functional limitations. [name] and her team study how the environment accounts for the differences between what individuals are capable of doing and their actual participation in society. The PEPL lab will provide study assessments, and research support including secured computer and storage spaces.

---

Two buildings of Shepherds senior apartments will collaborate with us to conduct this study. The Shepherds senior apartments resides in a medically underserved zipcode, and most of the residents aged 62 or over. The social service coordinator [name] will coordinate with us to provide space and time to recruit eligible participants.

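### The 60% recruitment criterion has no consistent denominator, so it can be missed on eligibility alone even if every eligible person consents

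*Combined protocol and SAP*

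**What the plan says.** Three sections describe recruitment on three bases.

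- **C1** makes reach part of the primary aim, with 60% recruitment and 80% retention. The base is the participants targeted, a term that is not defined.
- **F2** measures recruitment as the share of residents who are enrolled, and retention as the share of those enrolled who complete the programme.
- **D1** reports the single-group pilot per person screened: "The recruitment rate was 44% (11 enrolled out of 25 screened". The next sentence uses another enrolled count: "The retention rate was 89% (8 completed out of 9 enrolled".

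Entry has been tightened since the pilot (D1 against E2):

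- Age: 60 or over in the pilot; "age 70 or older" now.
- Falls in the past year: any slip, trip or fall, or simply being worried about falling, in the pilot; at least two falls, or a single fall with injury, now.
- Short Blessed Test: exclusion from 10 in the pilot; from 8 now.

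D1 adds that "Eight older adults completed the pilot study", with mean age 66.4 and SD 5.6. E1 supports the design with the statement that "Adapted LiFE has strong face validity, good feasibility, and minimal risk", without saying that the pilot admitted a different population. No section explains why the target is 60% or estimates how many of the people approached will qualify.

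**The concern.** Reach is a primary-aim criterion. E1 names estimation of recruitment as a purpose of the study, and B2 says that the results will inform whether to go on to the main trial. A single rate over residents, or over people screened, mixes those who do not qualify with those who qualify and decline. The first calls for wider sourcing or another look at the entry criteria; the second calls for changes to the offer or the consent approach. A shortfall on the combined rate does not show which.

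The target also lies above the pilot's 44%, although entry is now stricter on three counts. If ineligible people stay in the denominator, the criterion partly tests how common the entry profile is, and not whether people who have it will join.

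**Working it through.** **1. The pilot's own figures (D1).** Both stated rates reproduce, but from different enrolled counts:

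- Recruitment: 11/25 = 44.0%.
- Retention: 8/9 = 88.9%, stated as 89%.

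With one enrolled count throughout:

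- 11 enrolled: recruitment 11/25 = 44%, retention 8/11 = 72.7%, below the 80% in C1.
- 9 enrolled: recruitment 9/25 = 36%, retention 8/9 = 89%.

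Exact (Clopper–Pearson) 95% intervals for recruitment: 11/25 gives 24.4% to 65.1%; 9/25 gives 18.0% to 57.5%.

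**2. How many completers could have been 70 or over?** Inputs from D1: n = 8, minimum age 60, mean 66.4, SD 5.6. Allowing for rounding, the ages sum to at most 8 × 66.45 = 531.6 and the SD is at least 5.55.

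- Six aged 70 or over need a sum of at least 6 × 70 + 2 × 60 = 540, which is too large.
- Five need at least 5 × 70 + 3 × 60 = 530, which leaves at most 1.6 years. The spread is greatest if one person takes all of it: 60, 60, 60, 70, 70, 70, 70, 71.6. The squared deviations from 66.45 sum to 3 × 41.60 + 4 × 12.60 + 26.52 = 201.7, so the SD is √(201.7/7) = 5.37, below 5.55. Five is therefore impossible (with divisor n the SD is smaller still, 5.02).
- Four is possible: 60, 60, 60, 66, 70, 71, 71, 73 has mean 66.4 and SD 5.6.

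So at least 4 of the 8 completers were under 70 and would not qualify now.

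**3. What 60% requires if ineligible people stay in the denominator.** Let e be the share of that denominator who are eligible. Then recruitment = e × uptake, so the uptake needed is 0.60/e. The documents do not give e; the values below are assumptions that show the range.

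| e | Uptake needed among the eligible |
|---|---|
| 100% | 60% |
| 90% | 67% |
| 80% | 75% |
| 70% | 86% |
| 60% | 100% |
| 50% | 120%, impossible |

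If the denominator is eligible people, the requirement is 60% whatever e is. The choice of denominator thus decides what the criterion tests.

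**The case against.** The strongest reply is that C1's targeted participants may mean eligible people, in which case eligibility cannot cause a failure. That reading is possible. But the operational definition is in F2, which counts residents, and nothing in the text restricts these to eligible residents.

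A second reply is that sourcing may pre-select people who qualify. E2 2.a names referrals from occupational therapy staff and advisory board members as the main channels, and E2 2.c adds word of mouth and a previous study's control group. This stands: e could be high. It also fits poorly with a denominator of residents, since people referred in need not live in the collaborating buildings.

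A third reply is that the plan already discloses the pilot's entry criteria in full in D1 and calls the results only potential. That also stands, so D1 needs no restatement of the criteria. E1 nonetheless cites feasibility without the qualification.

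A reader might infer more than the documents support:

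- *At least half of the pilot's participants were under 70.* The age figures cover the completers only. The proven minimum among those enrolled is 4/11 = 36% or 4/9 = 44%.
- *The 44% can be scaled by the completers' age mix to forecast this trial.* The ages of the 25 people screened are not given, and D1 does not divide those not enrolled into ineligible and declined.
- *Most residents are too young.* I1 says only "most of the residents aged 62 or over"; the share aged 70 or over is not stated.
- *Low recruitment would show that Adapted LiFE is unacceptable.* Acceptance has its own criterion in C1 and its own satisfaction question in F2.

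**Conclusion.** Wrong as written, and more than a missing detail: C1 and F2 give different bases for a primary-aim criterion, and on F2's basis ineligible people count as recruitment failures. With that basis, or with people screened as in the pilot, 60% cannot be reached if fewer than 60% qualify, even with full consent. At 70% to 80% eligible, the real hurdle is 86% to 75% uptake and not 60%.

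The criterion can fail on eligibility; the documents do not establish that it will. The interval for 11/25 includes 60%. The interval for 9/25 stops just short of it, at 57.5%, but both describe a differently selected group. How far eligibility lowers the rate depends on e, which is unknown and which referral may raise. The age bound assumes that the pilot's minimum age of 60 was respected.

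The pilot is a weak precedent for two reasons: its entry criteria were looser on age, falls and cognition, and its enrolled count is given as both 11 and 9. Two people may have left between enrolment and the start of the programme, but D1 does not say so.

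**What to change.** - **C1 and F2:** define uptake = enrolled/eligible and apply the 60% criterion to it. Use the same terms in both sections.
- **F2:** report eligibility yield = eligible/screened separately, by criterion failed, with no threshold. Also count people who decline before their eligibility is known, so that uptake does not look better than it is.
- **D1:** reconcile 11 and 9 enrolled, and state recruitment and retention from one count.
- **E1:** do not use the pilot's rates as a benchmark for this population.
- **A1 and E2:** once eligible people form the denominator, the criteria must agree. The abstract words the fall criterion more loosely and lists a depression exclusion that E2 lacks; the two must be reconciled.

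No entry criterion has to change for this. Screening already collects age, number of falls and the Short Blessed Test (F 1.a), so the cost is one reason-for-failure field in the existing log plus wording. It should be in place before screening starts, because reasons not recorded then may not be recoverable. The downside is that the pilot support will read as less favourable.

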## D2 Dose Rationale and Risk/Benefits

The Adapted LiFE has an updated user manual but it retains the essential components and dose of the original LiFE (Table 2). In addition to practicing a set of structured exercise, participants learn to embed functional exercise activities into their daily routines that include balance and muscle strengthening training. For example, a participant could practice one-leg stands while waiting for food to heat up in the microwave. Participants also learn to gradually increase the difficulty of balance and muscle strengthening activities included in LiFE (see E3, and table 3).

Clinical trials of LiFE, where comparing LiFE to structured exercise program, indicated the risk of participating in LiFE is no more than minimal risk. The benefit of LiFE has been proven in past study indicating LiFE could reduce falls, enhance balance and muscle strength among older adults. We hypothesize Adapted LiFE will have the same effect as the original trial.

## **E Study Design**

[figure not shown]
### **E1 Overview of Study Design**

The pilot study will use RCT with an attentional control design (Figure 2). The purpose of the pilot study with the same design as the future main study is to test the study protocol, estimate recruitment/retention rate, and validate tools. This study design is appropriate for a future larger study because Adapted LiFE has strong face validity, good feasibility, and minimal risk when compared with structured exercise programs for medically underserved older adults.

We will recruit 16 participants and randomize them to receive 7 sessions of home visit and 1 booster phone call one month after the last session of Adapted LiFE or attention control (AC) intervention. Once an eligible participant is screened and consented in his/her home (T0 visit), the OT interventionist will either conduct or schedule the pre-test (T1). All pre- and post-tests will be conducted in participants' homes. After T1, the OT interventionist will randomize the participants to Adapted LiFE or the attention control group. The intervention period will start immediately after randomization and consist of seven sessions over 12 weeks. Post-tests (T2) will be conducted by a blinded OT rater after the last intervention session at the participant's home. Phone follow-ups (T3) will be conducted one month after post-test by a blinded OT rater. Any additional questions from the participants will also be addressed in the phone follow-up.

Feasibility outcomes such as reach, adherence, fidelity, and safety will be evaluated throughout the study session. Efficacy outcome such as balance and muscle strength will be evaluated at pre- test (T1), and post-test (T2). Habit formation will also be evaluated at T1, T2, and 1-month after post-test via phone.

*Figure 2. Overview of the feasibility pilot study*

### **E2 Subject Selection and Withdrawal**

#### **2.a Inclusion Criteria**

Medically underserved older adults will be recruited by convenience sampling. Referrals from OT staff and members of a community advisory board of the Participation,

---

Environment & Performance Laboratory (PEPL) will be the main channels for recruiting medically underserved older adults. Inclusion criteria include:

- (1) age 70 or older;
- (2) live independently;
- (3) live in a medically underserved/health professional shortage area;
- (4) self-report two falls or one injurious fall in the past 12 months. The definition of a fall and injurious fall are described in Table 4.

## **2.a Exclusion Criteria**

Exclusion criteria include:

- (1) Short Blessed Test score  $\geq 8$ , indicating cognitive impairment consistent with dementia;
- (2) inability to stand independently with a walking device;
- (3) having a serious health condition with a physician's order where exercise is contraindicated.

## **2.b Ethical Considerations**

We will use convenient sampling to recruit medically underserved older adults, and we will not limit the number of participants due to their race/ethnic background.

## **2.c Subject Recruitment Plans and Consent Process**

Purposeful sampling was used to recruit MU older adults in the greater St. Louis area. Potential participants will also be identified from the control group from a previous study. Participants will be recruited by word of mouth or at two Shepard senior apartment buildings (see letter of supports in attachments). Flyers will be distributed and study members will be available in the lobby and at events scheduled in the building to provide information on the study (study members will be contacted and invited by the building service coordinator).

Participants who are referred and contact study staff via phone or in person will be able to ask questions about the study procedures. If they are interested, study staff will start the screening process by phone or in person.

If the individual is eligible, a copy of the large-print informed consent document will be mailed or delivered, and an initial home visit will be scheduled. At the home visit, a trained staff member will obtain written informed consent.

To minimize the possibility of coercion or undue influence during the consent process, all elements of consent will be reviewed with older adults prior to enrolling in the study. Elements such as the purpose of the study, risks, benefits, alternatives to the study, how confidentiality will be maintained, the PI's contact information, no consequences to withdrawal, and how study results will be shared are written in plain language. In addition, all staff members have participated in cultural competence training and are trained to interview older adults, which is particularly important for older adults with low vision, or low literacy levels. Written informed consent to participate in the study will be obtained before any test or measurements are performed. The consent form will be signed by a witness and will be stored in the office of the PI under double locks.

---

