## **C Study Objectives**

### ***C1 Primary Aim***

The primary aim of this study is to establish feasibility of Adapted LiFE and a RCT design.

WE hypothesis that the feasibility pilot study will have high reach (60% recruitment and 80% retention rate of targeted participants), acceptance (80% of participants rating high satisfaction with Adapted LiFE), adherence (80% of all exercise activities achieved during the intervention period for each participant), fidelity (90% consistency of elements delivered by occupational therapists throughout the study period), safety (no adverse events caused by Adapted LiFE), and appropriate efficacy measurement selection (70% of the participants do not show floor/ceiling effects among balance, muscle strength, and habit outcomes at pre- and/or post-tests).

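### Recruitment and retention are pooled over new contacts and former controls of an unidentified earlier study, and earlier LiFE training is not excluded, so the Reach estimates may run high for the main trial

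*Combined protocol and SAP*

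**What the plan says.** Recruitment sources are spread over two sections. The inclusion section (E2 2.a) names referrals from occupational therapy staff and a community advisory board as the main channels, under convenience sampling. Section E2 2.c adds that "Participants will be recruited by word of mouth or at two Shepard senior apartment buildings", and then: "Potential participants will also be identified from the control group from a previous study". No number or share is attached to that last source, and the study is not identified. The only earlier study of Adapted LiFE described (D1) had a single group, so it had no control arm.

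There are four inclusion criteria (age, independent living, area of residence, falls history) and three exclusion criteria (cognition, ability to stand, and "having a serious health condition with a physician's order where exercise is contraindicated"). None concerns earlier study participation or earlier training in LiFE or Adapted LiFE.

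C1 sets the Reach target as "high reach (60% recruitment and 80% retention rate of targeted participants". E1 gives the pilot's purpose as to "test the study protocol, estimate recruitment/retention rate, and validate tools". F2 defines recruitment as the percentage of residents enrolled and retention as the percentage of enrolled participants completing the programme. Neither F2 nor G2 splits these by recruitment source.

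**The concern.** In an efficacy trial, mixing recruitment sources would be a minor point of generalisability. Here recruitment and retention are among the quantities the pilot exists to estimate. People who have already consented to research and been followed in it are selected for willingness to join and, if they completed, for staying. If they are pooled with newly approached people, the result describes a mixture whose weights the plan does not fix. The main trial may not have the same mixture; the documents do not say.

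A second, smaller gap is earlier training. Someone who completed the single-group Adapted LiFE pilot, is now 70 or older and meets the falls criterion could be enrolled. That person might bring an existing habit and trained balance to the pre-test, both of which are measured outcomes. At risk is the usefulness of the Reach figures for planning, and to a lesser degree the pre-post change in a sample of 16.

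**Working it through.** **Inputs from the documents.** Sample size 16 (G1, set without a calculation). Targets 60% and 80% (C1). Earlier pilot (D1): "The recruitment rate was 44% (11 enrolled out of 25 screened"; retention 8 of 9; mean age of completers 66.4, SD 5.6.

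**Reproducing the stated rates.** 11/25 = 44.0% and 8/9 = 88.9%, as printed. D1 counts 11 enrolled for recruitment but 9 for retention; 8/11 would be 72.7%. D1 therefore gives no secure retention baseline, and the retention rates below are assumptions.

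**Recruitment.** Let k of the 16 enrolled be former controls who enrol at rate p (assumed), and let the rest be new contacts enrolling at 44%. People approached = k/p + (16 − k)/0.44, and pooled rate = 16 / [k/p + (16 − k)/0.44].

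| k of 16 | p = 70% | p = 80% | p = 90% |
|---|---|---|---|
| 0 | 44.0% | 44.0% | 44.0% |
| 2 | 46.1% | 46.6% | 47.0% |
| 4 | 48.5% | 49.6% | 50.4% |
| 8 | 54.0% | 56.8% | 59.1% |
| 9 | 55.6% | 58.9% | 61.8% |
| 10 | 57.3% | 61.2% | 64.7% |
| 12 | 61.0% | 66.4% | 71.4% |

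Example: k = 9, p = 0.90 gives 9/0.90 + 7/0.44 = 10.0 + 15.9 = 25.9, and 16/25.9 = 61.8%. The 60% line is first crossed at k = 9 (p = 90%), k = 10 (80%) and k = 12 (70%). At p = 60% all 16 would be needed, and at p = 44% the shift is zero.

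**Retention.** With m of 16 from the earlier study, the expected rate is [m × r_old + (16 − m) × r_new]/16. The 80% target needs at least 13 of 16, since 0.80 × 16 = 12.8. The chance of meeting it is the exact sum of two binomials.

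| m of 16 | New 70%, former 95%: expected rate; chance of ≥13 | New 80%, former 90%: expected rate; chance of ≥13 |
|---|---|---|
| 0 | 70.0%; 0.25 | 80.0%; 0.60 |
| 2 | 73.1%; 0.34 | 81.3%; 0.65 |
| 4 | 76.2%; 0.45 | 82.5%; 0.70 |
| 8 | 82.5%; 0.70 | 85.0%; 0.79 |

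**Sampling error for scale (exact 95% intervals).** 13/16 = 81%: 54% to 96%. 16/26 = 62%: 41% to 80%. A shift of 2 to 6 points, from 2 to 4 participants, is small beside these.

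**Earlier Adapted LiFE training.** If ages in the single-group pilot were roughly normal (assumed), the share aged 70 or older at that time is P(Z > (70 − 66.4)/5.6) = P(Z > 0.64) = 0.26, about 2 of the 8 completers, and more as they age. The present falls criterion is stricter than the pilot's, so fewer would qualify.

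**The case against.** The strongest reply is that this source is only an additional one. Other channels are named as the main ones, and its share could be zero. That stands: a reader might infer that the pilot will be filled with proven volunteers and that Reach is overstated, but the documents give no share and no source-specific rates, so neither can be asserted.

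The assumed rates can also be challenged. The 44% is enrolled out of screened, from one building, under looser age and falls criteria, and has an exact 95% interval of 24% to 65%. A 90% rate on the same basis would require nearly all former controls to pass the stricter criteria and consent. This is why a range is shown, and why the upper end should not be read as likely. F2 also takes residents as the denominator of recruitment, so it is unclear whether former controls from elsewhere would be counted at all.

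A reader might also infer carry-over through the former controls. The plan does not support this: it does not say what they received or that the previous study tested LiFE, and a control group would ordinarily not have had the active programme. The firmer gap is the missing criterion for people already trained in LiFE or Adapted LiFE, although the plan does not propose recruiting them.

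Finally, Reach alone does not decide whether the main trial proceeds. C1 sets targets in several domains, and B2 says only that the results will inform the decision.

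What remains is that large sampling error does not excuse an avoidable bias, and source may not be recoverable if it is not recorded at screening. The screening log is appendix 2, which is not in the available text, so it may already hold this field.

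**Conclusion.** The concern holds in limited form. The plan allows an unstated share of participants to come from an unidentified study's control group, plans no report of recruitment or retention by source, and does not exclude earlier LiFE or Adapted LiFE training. An upward bias in Reach is plausible but unproven. It is zero if rates are equal across sources, about 2 to 3 points in recruitment if 2 of 16 come from this source, and enough to cross 60% only if 9 to 12 of 16 do. These recruitment figures rest on 44% for new contacts and an assumed 70% to 90% for former controls. For retention, the assumed 70% against 95% moves the chance of meeting the target from 0.25 to 0.45 with 4 of 16 from this source; with 80% against 90% the change is from 0.60 to 0.70. The remedy is justified because it is nearly free and bears on a quantity the pilot is meant to estimate, not because a large bias has been shown.

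**What to change.** 1. In E2 2.c, identify the previous study and describe its control condition.
2. Record recruitment source and earlier study participation for everyone screened, if the log does not already do so.
3. In F2 and G2, report recruitment and retention overall and separately by source, and state that the new-contact rate will be used to plan the main trial. Say whether former controls living elsewhere enter the recruitment denominator.
4. Add an exclusion for earlier training in LiFE or Adapted LiFE.

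Former controls need not be removed from the overall rate, and an exclusion for earlier Go4Life use is not needed on the evidence in the plan.

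The cost is at most two screening fields, one eligibility line and a few reporting sentences. The pool becomes slightly smaller, and the source-specific rates will be less precise than the pooled one, so they should carry exact confidence intervals.
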